Patient Participants: Inclusion criteria are: 1) age ≥ 18 years, 2) score on the Generalized Anxiety Disorder [GAD-7] scale equal to or greater than 8, and 3) ability to speak English. Exclusion criteria are: 1) other psychological conditions rendering the person unlikely to benefit from a brief treatment, including psychosis, bipolar disorder, cognitive impairment, and active substance abuse or dependence (comorbid depression permitted); 2) current suicidal ideation or intent; 3) past suicide attempt or psychiatric hospitalization; 4) concurrent receipt of regular individual psychotherapy; 5) use of anxiolytic medication (including benzodiazepine and tranquilizers; antidepressants okay).

Maximum number of subjects

Enter the total maximum number of subjects to be recruited and enrolled 30-32

*required

Provide the enrollment breakdown number for each participant population

For example: n = 5 teachers, n = 30 students

Coaches: 5-7; Patient participants: up to 25

*required

What are the selection criteria for research participants?

Include sample size calculations, if applicable.

This exploratory pilot study will rely on convenience sampling. Coach participants (n = 5-7, to allow for attrition) will be recruited from the UNLV department of psychology and related departments. Patient participants (up to n = 25) will be recruited from the UNLV PRACTICE, UNLV campus, and the general community (see below).

This is a single-arm trial focused on feasibility and acceptability as well as preliminary clinical response (e.g., improvement in anxiety symptoms, engagement of purported psychological mechanism of avoidance) for a future R-series application to NIMH. There is no power analysis for such exploratory work; the sample sizes are not powered to detect treatment effects or statistical significance. Rather, these sample size estimates are determined by prior literature to demonstrate proof-of-concept and identify preliminary feasibility, acceptability, and appropriateness alongside initial demonstration of clinical impact.

See inclusion/exclusion criteria above for further details.

*required

Vulnerable Populations

Please check the population(s) that will be enrolled. Check all that apply.

Pregnant Women/Fetuses/Neonates

Minors with Parental Permission

	Minors who can consent themselves
	Prisoners
	Other
✓	None of the Above
*required	
Are yo	u excluding your populations based on gender, race or ethnic origins?
	Yes
✓	No
*required	

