The PI and research team will maintain regular contact with all coach participants. Coaches will be supervised by the PI (a licensed psychologist) on a weekly basis while carrying an active caseload and will be able to contact their supervisor outside of that time whenever necessary. Weekly supervision will involve discussion of ways in which coach participants can cope effectively with patient distress. Supervision will include group supervision, in which coaches will present cases identified only by Study ID number. Such desire for group supervision was expressed by similar student coaches in the PI's former trial of a similar nature (conducted at the University of Washington; these experiences from student coaches were published in Woodard, Mraz, & [name], 2023, BMC Psychiatry).

Research staff will always be present on campus and the PI will be available by phone when coaches meet with patient participants. In addition, as part of standard protocol the PI will be reachable at all times during the week, evening, and weekend if necessary via cell phone.

The PI will train research assistants and coaches in an emergency protocol (attached risk of harm protocol). The existing protocol the PI has used in related work with lay volunteers and other nonspecialists/coaches is as follows: If patients report any thoughts of committing suicide or harming themselves, worsening of mental health symptoms, emergent manic or psychotic symptoms, thoughts of homicide or harming others, or elder or child abuse/neglect during or outside of STAR sessions, coaches immediately contact the PI. The PI will conduct a risk assessment with the patient participant and will arrange emergency psychiatric services, contact police, or place a report to child or elder abuse services if indicated. Coaches only see patient participants during hours when our research group in on campus; the PI is always aware of these meetings and will be available during these times and are reachable via phone.

The research team has agreed to abide by the confidentiality and data protection rules of the study outlined above. Investigators will not share information regarding intervention fidelity with other coaches or study staff.

Patient participants: The following safeguards will be implemented to increase the safety of patient participants:

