(a) Clinical deterioration and suicide risk: We will attend to clinical deterioration for both participant protection purposes, and in order to document the safety of the intervention. We define "clinical deterioration" as 1) the development of passive or active suicidal ideation (as confirmed by investigators) at any point during the study; 2) the development of manic or psychotic symptoms; or 3) ≥30% increase in PHQ-9 or GAD-7 scores at follow-up assessment. Rating scales may not adequately capture clinical deterioration in all patients. For this reason, we will encourage coaches to report when they notice a worsening of clinical state that is not identified by the above criteria.

Any patient participant exhibiting \geq 30% increase in GAD-7 scores for two consecutive sessions will trigger specific case-focused individual supervision with [name], which may include specific guidance on following sessions, outside recommendations, and/or direct contact of [name] with the patient.

Despite excluding individuals with active suicidality at screening, a patient participant may later (at sessions 2-8) endorse item 9 on the PHQ (reporting having "Thoughts that you would be better off dead, or thoughts of hurting yourself in some way?"). This is unlikely to happen but is possible. This will be handled on a case-by-case basis and a positive answer endorsement to item 9 is not necessarily indicative of active suicidality (e.g., there may be thoughts of death but not actually wanting to die/kill oneself). Any patient participant who endorses PHQ-9 item 9 (suicidal ideation) will trigger the coach to conduct the C-SSRS (Columbia Suicide Severity Rating Scale). Any indication of moderate or high risk will trigger the PI to immediately telephone and evaluate the patient participant to determine presence of suicidal ideation and level of risk. Also, any client exhibiting \geq 30% increase in PHQ-9 scores for two consecutive sessions will trigger specific case-focused individual supervision with [name], which may include specific guidance on following sessions, outside recommendations, and/or direct contact of [name] with the patient.

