Patients with current suicidal ideation or a history of suicidal behavior will be ineligible to participate in this study. Individuals who develop active suicidal ideation will be removed from the study and referred to the crisis line, their PCP, and other relevant clinical services by the PI. Patients who develop passive suicidal ideation or who evidence \geq 30% increase in PHQ-9 or GAD-7 may be permitted to remain in the study and receive the intervention; they will also meet with the PI to discuss appropriate treatment recommendations (e.g., PCP, the UNLV PRACTICE, other resources). Investigators will follow up to ensure this connection takes place. This may include obtaining permission from the patient ppt for the PI to contact the PCP to discuss the clinical concerns and assist the PCP in management recommendations. Study research coordinators are trained to assess manic and psychotic symptoms and will conduct follow up assessments.

In non-emergent cases of active ideation (e.g., nonspecific thoughts of wanting to kill oneself), the patient participant will be allowed to continue with the day's planned coaching session and any scheduled assessments, as more information (e.g., from a clinical interview) may assist with better understanding and documenting the worsening. If the patient participant does not continue with a scheduled assessment because of PI discretion, they will still receive payment for their next scheduled assessment (either same-day or otherwise close in time; e.g., scheduled Week 8 assessment and PI withdraws patient participant after week 6 or 7 session).

b) Risk associated with intervention: The STARS program is a brief, structured behaviorally-based mental health intervention that is based on and informed principles from cognitive behavioral therapy (CBT), a well-known and extensively researched treatment paradigm for depression and

anxiety. The PI is a licensed clinical psychologist, clinical supervisor, and graduate faculty instructor with specialty in CBT and clinical trials conduct. To limit distress, research personnel and coaches will be trained and supervised by the PI in procedures for helping patients cope with protocol-generated concerns, stress, and anxiety.

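### The 30% worsening rules name no reference score and, counted from Session 1, cannot be met by GAD-7 starts of 17-21 or PHQ-9 starts of 21-27

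*Protocol*

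**What the plan says.** The rules are in the protocol's section on preventing and minimizing risk, patient participants, item (a) on clinical deterioration and suicide risk. A 30% rise appears there in three roles.

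- **Definition.** One of three forms of clinical deterioration is a 30% or greater "increase in PHQ-9 or GAD-7 scores at follow-up assessment". Deterioration is tracked to protect participants and also "in order to document the safety of the intervention".
- **Session trigger.** A 30% or greater "increase in GAD-7 scores for two consecutive sessions will trigger specific case-focused individual supervision". The PHQ-9 has a matching rule: an "increase in PHQ-9 scores for two consecutive sessions will trigger specific case-focused individual supervision".
- **PI meeting.** Patients with a 30% or greater "increase in PHQ-9 or GAD-7 may be permitted to remain in the study and receive the intervention", and they also meet the PI about treatment recommendations.

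None of the three names the score from which the rise is counted, and none sets a minimum point change or an absolute level. Entry requires a "score on the Generalized Anxiety Disorder [GAD-7] scale equal to or greater than 8", with no upper limit. Comorbid depression is allowed but not required, so the PHQ-9 has no entry minimum.

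The protocol also has safeguards that do not use the 30% figure. After the definition it says that "we will encourage coaches to report when they notice a worsening of clinical state that is not identified by the above criteria". The emergency procedure tells coaches to contact the PI at once if patients report, among other things, "worsening of mental health symptoms, emergent manic or psychotic symptoms". The PI reviews session scores and supervises weekly.

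**The concern.** A percentage rule on a bounded scale fails at the top: the higher the start, the larger the rise demanded and the less room there is for it. In an anxiety trial, the patients out of reach on the GAD-7 are the most anxious. At the bottom of the PHQ-9 the rule is very easy to meet, and at 0 it is undefined.

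The missing reference score adds to this. The GAD-7 is taken at telephone screening and again at every session, so a coach could count from screening, from Session 1 or from the previous session. Who can trigger the rule depends on that choice.

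At stake is a score criterion that serves both protection and safety documentation. If that documentation reports few or no 30% rises among severe starters, part of the reason may be that none was possible.

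**Working it through.** The plan states no derived figure to reproduce, so this is a direct check of the rule.

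**Inputs.** Threshold 30% (protocol, risk section). GAD-7 has 7 items and PHQ-9 has 9 (protocol, First STARS Session). Item scoring is not printed; 0-3 per item is assumed, giving maxima of 21 and 27. GAD-7 at entry is 8 or more. Up to 25 patients, minimum 15.

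**Step 1: lowest qualifying score from Session 1.** This is 1.3 × start, rounded up to a whole number.

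| Scale (maximum) | Start → score needed | Reachable? |
|---|---|---|
| GAD-7 (21) | 8→11, 10→13, 16→21 | yes |
| GAD-7 (21) | 17→23, 18→24, 19→25, 20→26, 21→28 | no |
| PHQ-9 (27) | 1→2, 2→3, 3→4, 4→6, 7→10, 20→26 | yes |
| PHQ-9 (27) | 21→28, and higher up to a start of 27 | no |
| PHQ-9 (27) | 0 | percentage undefined |

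The cut-off follows from 21/1.3 = 16.15 and 27/1.3 = 20.8. Eligible GAD-7 values run from 8 to 21, which is 14 values, and 5 of them (36%) are out of reach. PHQ-9 starts of 1-3 qualify on one point. The session trigger needs that point at two consecutive sessions; the follow-up definition needs it once.

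**Step 2: does the reference matter?** Suppose the rule is read session to session, with a 30% rise at each of two sessions. A GAD-7 start of 12 goes to 16 and then 21, which is reachable. A start of 13 goes to 17 and then 23, which is not. The unreachable starts widen from 17-21 to 13-21 on the GAD-7, and from 21-27 to 16-27 on the PHQ-9.

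**Step 3: how many patients?** The documents give no Session 1 distribution, so a normal distribution discretised to 8-21 is assumed.

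| Assumed mean, SD | Share at 17 or more | Of 25 |
|---|---|---|
| 11, 3 | 3.8% | about 1 |
| 11, 4 | 10.0% | 2.5 |
| 11, 5 | 15.9% | 4.0 |
| 13, 4 | 19.4% | 4.9 |
| 15, 5 | 34.1% | 8.5 |

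With the minimum of 15 patients, the mean-11 rows give 0.6 to 2.4.

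**Step 4: what a reachable criterion would gain.** The model is 8 sessions, independent normal error with SD 2 (assumed), and scores rounded and clipped to the scale. Take patients with a true GAD-7 start of 17-18, the same error at Session 1, and a sustained true rise of 3 points. The current two-session trigger fires in about 21-31%, all in patients whose observed Session 1 score fell to 16 or below. A 3-point criterion at observed starts of 17-18 would raise this to 55-58%. Requiring the maximum of 21 asks for 4 points from 17 and 3 from 18. Its detection therefore lies between those two sets of figures, and its chance triggers cannot exceed those of the 3-point criterion.

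**The case against.** The strongest reply is that the plan foresees the limitation. It concedes that rating scales may miss deterioration, asks coaches to report what the criteria miss, sends reported worsening to the PI at once, and has the PI monitor session scores and supervise weekly. Suicidal ideation and manic or psychotic symptoms count as deterioration at any score. All of this stands. A reader might infer that severe starters go unmonitored, and the documents do not support that. What the safeguards lack is a GAD-7 criterion that these patients can reach.

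A second reply is that no deterioration count is specified. The SAP has no deterioration outcome, and the protocol does not say whether coach-reported worsening enters the safety documentation. This also stands, so the point concerns a printed definition used for documentation, not a planned endpoint.

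Third, Session 1 is the natural reference, and for the PHQ-9 it is the first score listed. The attached Risk of Harm Protocol and Assessment Schedule are not in the supplied text and may name it. That could settle the reference, but not the arithmetic in Step 1.

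Fourth, a reader might infer that the current rule detects nothing in truly severe patients. The 0% holds only for an observed Session 1 score of 17-21. For true starts of 17-18 measured with error, the like-for-like figure is the 21-31% in Step 4.

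Fifth, a reader might treat the low end of the PHQ-9 as a large false-alarm problem. With starts of 1-3 and no true change, the two-session trigger fires by chance in 57% at SD 2, but only if Session 1 is error-free. With equal error at Session 1 it is 16-39%. The stated consequence of the session trigger is extra supervision, and nothing in the documents shows how many patients would start there.

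**Conclusion.** The concern holds as a gap in the numeric rule. The reference score is unstated in the supplied text. Counted from Session 1, GAD-7 starts of 17-21 and PHQ-9 starts of 21-27 can never meet a 30% rise, and a PHQ-9 start of 0 has no defined percentage. The arithmetic rests only on 0-3 item scoring.

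The number of patients rests on assumed scores. About 1 to 4 of 25 is the range closest to the stated mild-to-moderate target. The 8.5 of 25 at mean 15 fits that target poorly and is an upper illustration. The consequence is limited: monitoring continues by other routes, and what suffers is the score criterion and the safety record that uses it. This is a low-priority change, worth making because it is cheap.

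**What to change.** In item (a), for the definition, both session triggers and the PI meeting:

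1. State that the rise is measured *from the Session 1 score*. Keep 30% and the two-session condition.
2. Where 30% exceeds the maximum but at least 3 points of room remain (GAD-7 17-18, PHQ-9 21-24), let reaching the maximum (21 or 27) count. A GAD-7 start of 16 already needs 21 and a PHQ-9 start of 20 needs 26, so a higher start never qualifies at a lower score. A flat 3-point rule would break this: 17 would qualify at 20 while 16 still needs 21.
3. For GAD-7 19-21 and PHQ-9 25-27, have the PI review the case at weekly supervision and record deterioration by judgement, as part of the definition.
4. For a PHQ-9 start of 0, state a point rise, for example 3. Without the option below, a start of 1 still qualifies at 2; a 2-point rise from 0 would keep the order.

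**Option only:** require at least 3 points for PHQ-9 starts of 1-6. At starts of 1-3 and SD 2, this cuts chance triggers from 57% to 6% if Session 1 is exact, but only from 16-39% to 11-22% with equal Session 1 error. At SD 3 with that error there is no gain. For starts of 1-6, detection of a sustained 3-point rise falls from 98-100% to 86% with Session 1 exact.

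**Cost:** a few sentences, no new data, and a few extra supervision reviews. At true GAD-7 starts of 17-18 with no true change, a 3-point criterion would fire by chance in 6-10% at SD 2 (0-23% over SD 1-3), and the maximum-score criterion no more often. With at most 4.8 of 25 patients starting there, that is at most 4.8 × 0.10 = 0.5 patients (4.8 × 0.23 = 1.1 at SD 3). Starts of 19-21 still have no score criterion, only recorded judgement. The documents give no reliability figure for either scale, so the 3-point values are a practical choice: 30% already requires 3 points at starts of 7-10.

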TREATment Lab staff, research assistants, and graduate students are trained and supervised by the PI, a licensed clinical psychologist, to conduct these screenings. They also receive supplemental training such as video tutorials in proper admiration of the Columbia Suicide Severity Rating Scale (e.g., https://www.youtube.com/watch?v=sWX3lk2AoxU)

Coach Participant Assessment. Primary assessment of coach participants will occur through observation of their performance in role plays and STARS sessions. Coach participants will be paid \$10 per session completed with a patient participant (x 8 sessions = up to \$80 per patient). They will also be invited to participate in a post-study qualitative interview. We request flexibility in this exit interview, per the standards of qualitative methodology (see attached coach interview guide). The interview will last no longer than 60 min and will be audio recorded for transcription by a third party. The transcripts will be deidentified and audio files will be deleted after transcription. The interview will be conducted by a TREATment lab research assistant(s). The interview will focus on the coach participant's experience (1) learning the intervention, (2) delivering the intervention, and (3) other comments about the intervention or implementation. Coaches will receive \$50 for participation in the exit interview.

*required

What is the anticipated time commitment involved for each study procedure (e.g. 30 minutes for the survey, 1 hour for the interview, etc.)? What is the total time that each participant will spend in the entire study?

Describe the duration of study participation (i.e. the anticipated amount of time commitment required for each subject), the length and number of study visits, and the timetable for study completion.

Describe, in timeline sequence, the activities participants will be asked to perform specifically for the research, and how much time each activity will take. Attach your schedule of assessment, if applicable.

Event	Time
Eligibility Screening	Half-hour
Baseline Assessment	1.25 hours
STARS Session 1	Up to 1 hour
STARS Sessions 2-8	30 min each = 3.5 hours
Post-Treatmen Assessment	t Up to 1 hour (expected 45-60 min)
Follow-up 1 (6 weeks after completion of STARS)	Up to 1 hour (expected 45-60 min)
Follow-up 2 (12 weeks after completion of STARS)	TUp to 1 hour (expected 45-60 min)
Total	9-10 hours over 20 weeks

Schedule of assessment (if applicable)

Assessment Schedule_STARS_v2.0.docx

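### The protocol gives two different rules for assessing suicidal thoughts reported during the study, and no stated step confirms a low-risk report for the deterioration count

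*Protocol*

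**What the plan says.** Three places in the Protocol govern a patient who reports suicidal thoughts after enrollment.

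- **Risk-minimization procedures, coach participants (emergency protocol).** The trigger is broad: "If patients report any thoughts of committing suicide or harming themselves, worsening of mental health symptoms", followed by further emergencies. The response is: "coaches immediately contact the PI. The PI will conduct a risk assessment with the patient participant". No risk level has to be reached first. The rule is introduced with: "The existing protocol the PI has used in related work with lay volunteers and other nonspecialists/coaches is as follows".
- **Risk-minimization procedures, patient participants, item (a).** "Any patient participant who endorses PHQ-9 item 9 (suicidal ideation) will trigger the coach to conduct the C-SSRS". The PI's part is then conditional: "Any indication of moderate or high risk will trigger the PI to immediately telephone and evaluate the patient participant". The stated purpose of that call is to establish whether ideation exists and how serious the risk is.
- **Research Methods, Risk of Harm Protocol.** During the study, an item 9 score of 1 or more, or any ideation the patient reports, leads to a C-SSRS. The rater assigns low, moderate or high risk. Instructions for each level are left to an attached Risk of Harm Protocol, which is not among the documents available here.

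Item (a) also defines clinical deterioration, partly to document the intervention's safety. Its first criterion is "the development of passive or active suicidal ideation (as confirmed by investigators) at any point during the study". The text after item (a) lets patients who develop passive ideation remain, with a PI meeting about treatment recommendations. Patients who develop active ideation are to be removed.

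**The concern.** The coaches are undergraduates or recent graduates, and this is the most serious situation they are likely to meet. On a plain reading, they have one instruction to call the PI for any report, and another to administer an instrument themselves and involve the PI according to its result.

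The safety record is the second issue. A deterioration criterion that depends on investigator confirmation needs a confirmation step that works the same way for every report. If the step is described for some risk levels only, whether a low-risk report counts may depend on which instruction was followed and not on what the patient experienced.

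**Working it through.** The documents state no figure on this point, so the check is mainly a comparison of the text.

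**1. The rules side by side**

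| | Emergency protocol (coach safeguards) | Item (a) (patient safeguards) | Research Methods |
|---|---|---|---|
| Trigger | Any reported suicidal or self-harm thought | PHQ-9 item 9 endorsed | Item 9 score of 1 or more, or any self-reported ideation |
| First assessor | PI, once contacted by the coach | Coach, using the C-SSRS | C-SSRS; administrator during the study not named |
| PI evaluation at low risk | Required | Not stated | Left to the attachment |
| PI evaluation at moderate or high risk | Required | Required | PI contact provided for (screening paragraph) |

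The triggers overlap. Item 9 itself asks about self-harm, and the Research Methods rule takes in spoken disclosures as well as questionnaire answers. The same patient can therefore fall under both rules. At moderate or high risk they end in the same place, a PI evaluation. At low risk they differ on the first assessor and on whether the PI must evaluate.

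**2. Confirmation**

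- The deterioration criterion requires confirmation by investigators but names no method.
- The only PI step described as determining whether ideation is present is the telephone evaluation, which is tied to moderate or high risk.
- The later PI meeting for passive ideation concerns treatment recommendations. It presupposes that passive ideation has already been established.
- So no stated step turns a low-risk report under item (a) into a confirmed or an unconfirmed case.

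**3. Scale**

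Inputs: a minimum of 15 and a maximum of 25 patients (Research Methods, Recruitment and Training of Coaches).

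One patient classified differently changes the deterioration proportion by 1/N:

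- N = 25: 1/25 = 4.0 percentage points
- N = 15: 1/15 = 6.7 percentage points

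The documents give no rate of low-risk reports. For an assumed rate p, the same for each patient and independent between patients, the chance that at least one patient falls where the rules diverge is 1 − (1 − p)^N:

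| Assumed p | N = 15 | N = 25 |
|---|---|---|
| 5% | 1 − 0.95^15 = 53.7% | 1 − 0.95^25 = 72.3% |
| 10% | 1 − 0.90^15 = 79.4% | 1 − 0.90^25 = 92.8% |
| 20% | 1 − 0.80^15 = 96.5% | 1 − 0.80^25 = 99.6% |

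This is the chance that the conflict arises at all under the assumed rate. It is not the chance that a case is lost or miscounted.

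**The case against.** The best defence is that the passages were not meant to compete. The emergency rule is introduced as one used in related work and covers a broad list of emergencies, including homicide and abuse. Item (a) handles a single questionnaire item that, as it says itself, need not indicate active suicidality. A coach could give the C-SSRS and also call the PI. The attached Risk of Harm Protocol, on which coaches are to be trained, may already hold one rule for all risk levels.

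Part of this stands: the attachment may well resolve the matter in practice. It does not remove the conflict in the Protocol's own text. The emergency rule is given among this trial's safeguards, directly after the statement that coaches will be trained in an emergency protocol. Nothing says the two rules apply together, and if they did, item (a)'s threshold would govern only the timing or form of the PI's contact, which should then be stated.

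Four stronger inferences are tempting, and the documents do not support them.

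- *Low-risk reports never reach the PI.* The PI uses PHQ-9 scores to monitor response and adverse events, receives session recordings and scores, supervises coaches weekly, and meets patients who develop passive ideation. The gap is in confirmation, not visibility.
- *Coaches are untrained for this.* The Research Methods sentence "TREATment Lab staff, research assistants, and graduate students are trained and supervised by the PI" concerns these screenings and does not name coaches. The coach safeguards, however, say the PI will train coaches in the Risk of Harm Protocol. Training in giving the C-SSRS is not separately described, but the training outline is an attachment that cannot be seen here.
- *A given number of patients will be miscounted.* That would need a rate of low-risk reports and a rate of non-confirmation. The documents give neither.
- *A planned analysis is biased.* The SAP contains no deterioration or safety analysis. Removal for active ideation could lower the SAP's retention proportion, but the Protocol does not say which C-SSRS risk level active ideation receives, so no effect of the low-risk conflict on retention can be shown.

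**Conclusion.** The contradiction is real and confined to patients rated low risk. For them the Protocol gives two answers on who assesses first and on whether a PI evaluation is required, and it has no stated step by which their ideation is confirmed for the deterioration definition. The consequence is an ambiguous instruction to coaches and a safety record that may depend on the route taken. No efficacy result is affected.

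Each patient whose classification turns on the route is worth 4.0 to 6.7 percentage points of the deterioration proportion. That size follows from the planned 15 to 25 patients alone. How many patients are involved, if any, is unknown. The conclusion rests on the Protocol text as available; the attached Risk of Harm Protocol could narrow the practical problem, but the text would still need to agree with it.

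**What to change.** 1. **Reconcile the text.** The sponsor should align the Research Methods Risk of Harm section, the emergency protocol under the coach safeguards, item (a) with the text that follows it, and the attached Risk of Harm Protocol. One rule should cover every risk level, say who administers the C-SSRS during the study, and say who confirms ideation and how. Which clinical rule is right is for the sponsor to decide.
2. **Supplement the safety count.** Keep the investigator-confirmed definition. Beside it, tabulate from the database every patient with a new PHQ-9 item 9 score of 1 or more and every positive C-SSRS during the study, with confirmed cases shown as a subset. New should mean relative to session 1, when the PHQ-9 is first given; otherwise an endorsement already present at session 1 would count as a development. List separately any confirmed case that has neither an item 9 score nor a C-SSRS, such as a spoken disclosure that went straight to the PI.

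The cost is Protocol wording and one descriptive table. Item 9 scores are already entered after each session, and study records are to be held in REDCap. The small downside is that the table will include endorsements that are not true suicidal ideation, which is why the confirmed subset should be kept and labelled.
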